- Net area under the curve (netAUC) of postprandial glucose as measured by CGM in the 6 hours following the start of first meal. netAUC (mg/dL*min) will be calculated using a trapezoidal method [76], which sums all CGM values in the 6 hour period following the meal above the starting glucose and subtracts CGM values below the starting glucose.
- Percent of time with sensed glucose <70 mg/dl
- Percent of time with sensed glucose between 70 – 140 mg/dl
- Mean sensed glucose
- Percent of time with sensed glucose <54 mg/dl
- Percent of time with sensed glucose >180 mg/dl
- Percent of time with sensed glucose >250 mg/dl
- Mean amount of insulin delivered (in units and units/kg)
- Mean amount of pramlintide delivered (in mcg and mcg/kg)
- Coefficient of variation
- LBGI
- HBGI
- Safety endpoints (over full study duration):
 - Adverse events
 - Number of adverse events probably or possibly associated with pramlintide administration (see ‘Causality Relationship’ below)
 - Baxter Retching Faces (BARF)/VAS scale for gastrointestinal issues after first and second meal, see Protocol Appendix D.
 - Mean duration of gastrointestinal issues after first and second meal as reported by participant on BARF/VAS scale, see Protocol Appendix D.
 - Episodes of carbohydrate intake to treat hypoglycemia (defined as 15g carbohydrate intake)
 - Episodes of hypoglycemia defined as CGM <70mg/dL for 10 minutes or more
 - Number of provider-administered insulin injections due to hyperglycemia

Study Type

This is a single-center, crossover trial designed to evaluate glucose outcomes of a fully closed-loop system with insulin+pramlintide dosed in response to meal detection as compared to an insulin alone fully closed loop system.

Study Population

Study population will be adults with type 1 diabetes, ages 18 – 70 years of age. Younger participants are excluded as it is appropriate to assess safety first in the over 18 year old population. We are targeting a total of 35 participants to complete the full study protocol.

[figure not shown]
Power Analysis

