A sample size of 35 participants provides 90% power to detect a standardized paired mean difference of 0.56 SD, or 80% power to detect a 0.49-SD difference with a two-sided test at the .05 level of significance. This is calculated using a paired t test to approximate a mixed model with treatment, period, and sequence effects. Data from a previous study [24] showed a 0.64-SD reduction with pramlintide in 4-hour postprandial AUC for participants with >40 U bolus insulin per day. We plan to recruit more than half of our study participants from this population and so we expect to observe a slightly smaller reduction in AUC.

Protocol Summary:

Participants will undergo two study visits to evaluate (1) insulin+pramlintide versus (2) insulin-only delivery strategies. The order of the visits will be randomized. Meal scenarios will be identical across all study arms. Participants will arrive at approximately 7:30 am for all visits, be monitored through the afternoon and discharged at approximately 8 pm. During each study visit, participants will wear Omnipod(s) to deliver insulin and/or pramlintide and a Dexcom G6 CGM to measure glucose and a Polar M600 to measure activity levels. See Figure 1 and 2 below.

Figure 1: Study flow diagram

Time	Activity	Hours post meal
7:30 AM	Begin closed loop study	0
8 AM	Breakfast	1
9 AM		2
10 AM		3
11 AM		4
12 PM		5
1 PM		6
2 PM	Lunch	1
3 PM		2
4 PM		3
5 PM		4
6 PM		5
7 PM		6
8 PM	Discharge	

Figure 2: Treatment visit timeline

Subject Criteria

Inclusion Criteria:

1. Diagnosis of type 1 diabetes mellitus for at least 1 year.
2. Participants 18 to 70 years of age.
3. Current use of an insulin pump for at least 3 months with stable insulin pump settings for >2 weeks. OR Current use of multiple day injection insulin therapy with stable doses for >2 weeks.
4. Uses a carbohydrate ratio, at least occasionally, to dose meal time insulin
5. HbA1c \leq 10.5% at screening.
6. Total daily insulin requirement is less than 139 units/day.
7. Willingness to follow all study procedures, including attending all clinic visits.
8. Willingness to sign informed consent and HIPAA documents.

Exclusion Criteria:

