We will estimate the difference between systems using a fixed effect in a standard 2x2 crossover model with a random participant effect. We will also control for sequence (AB or BA) and period (1 or 2), though we do not anticipate statistically significant effects for these parameters.

We anticipate that the primary outcomes will be approximately normally distributed. We will review the appropriateness of this assumption using both goodness-of-fit tests and diagnostic plots, such as quantile-normal plots. If the normality assumption holds, possibly with a transformation of the outcome, we will test the difference between the study arms using a paired t-test. In the case of mild departures from normality or unequal variances at the two time points, we will re-analyze the primary outcome as the difference between the two visits using bootstrapped standard errors, which avoid distributional assumptions. We will use two-sided tests at the 0.05 level of significance.

Missing data: Missing sensed glucose values will be interpolated for up to 30 min segments. Longer periods of missing data will be omitted if they represent <3% of observation time (which will be truncated if a participant leaves the study early). If the missing data are >3% of observation time, we will use available CBG values to interpolate or impute using measurements. In the case that >2 participants fail to complete the study, we will analyze the primary outcome under multiple imputation using baseline values.

Confidentiality and Protection of Human Subjects

RISKS and BENEFITS

Risks: The risks of the protocol procedures are considered minor. Nonetheless, since pumps and sensors used within automated glucose control systems are imperfect, there is a risk for hyperglycemia and hypoglycemia. All studies will have frequent glucose and ketone samplings and a member of the study staff will be present for studies with a study investigator on call at all times.

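### The treatment effect is estimated from a period-adjusted crossover model but tested with a paired t-test that has no period term, and the choice of test has no stated rule

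*Combined protocol and SAP*

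**What the plan says.** In the combined protocol and SAP, the Statistical methods section starts with a model: "We will estimate the difference between systems using a fixed effect in a standard 2x2 crossover model with a random participant effect". It adds sequence and period to that model and remarks that neither is expected to be statistically significant.

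The next paragraph turns to testing. Normality is to be reviewed with goodness-of-fit tests and plots. If it holds, perhaps after transforming the outcome, "we will test the difference between the study arms using a paired t-test". If there is slight non-normality or unequal variance, the outcome is re-analyzed as the difference between visits with bootstrapped standard errors. The section gives no cut-off for the review, no list of permitted transformations and no rule for larger departures. It does not say which result is primary.

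The Power Analysis section gives the paired t a different role. The calculation was done "using a paired t test to approximate a mixed model with treatment, period, and sequence effects". There the mixed model is the analysis and the paired t stands in for it.

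**The concern.** A paired t-test on the within-participant differences has no period term. Any systematic shift between visit 1 and visit 2 goes into the error term. When the two sequences differ in size, part of the shift also goes into the contrast being tested. The crossover model removes the shift from both. Effect size and p-value would then come from different analyses of the same data, and a reader could see an estimate that the p-value does not match.

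The open selection step adds to this. Two analysts following the text faithfully could choose different scales or tests and report different primary p-values.

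**Working it through.** **Inputs from the documents.** N = 35 completers (Study Population); two-sided 0.05; 90% power at 0.56 SD and 80% at 0.49 SD of the paired difference (Power Analysis). Visit order is randomized, with no ratio or blocking stated (Protocol Summary).

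**Assumed.** The period effect π (shift from visit 1 to visit 2, in SDs of the paired difference) and the sequence split. The documents give neither, so ranges are shown.

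**Step 1: the plan's own figures.** For a paired t, the noncentrality is d√35 on 34 df. At d = 0.56, power is 0.896. At d = 0.49, it is 0.804. Both stated figures reproduce.

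**Step 2: the crossover test.** The treatment contrast is the mean of the two sequence means, on 33 df. The effective sample size is 4/(1/n₁ + 1/n₂).
- Equal sequences: power 0.803 at 0.49 SD and 0.895 at 0.56 SD.
- 21/14: 4/(1/21 + 1/14) = 33.6, noncentrality 0.49 × √33.6 = 2.84, power about 0.79.

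**Step 3: power of the paired t with a period effect.** Write each difference as D = τ ± π + e, with SD(e) = 1 and the sign set by sequence. Simulation with an 18/17 split, τ = 0.49 and at least 60,000 trials per setting gives:

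| π (SD) | paired t | crossover test |
|---|---|---|
| 0 | 0.80 | 0.80 |
| 0.2 | 0.80 | 0.80 |
| 0.3 | 0.79 | 0.80 |
| 0.4 | 0.78 | 0.80 |
| 0.5 | 0.76 | 0.80 |
| 0.8 | 0.66 | 0.80 |

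Hand check at π = 0.5. The expected sample variance is 1 + 0.25 × (35/34) × (1 − 1/35²) = 1.257, so S = 1.121. The mean difference is 0.49 + 0.5/35 = 0.504. Power ≈ Φ(0.504 × √35 − 2.032 × 1.121) = Φ(2.983 − 2.278) = Φ(0.705) = 0.76.

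The table takes the sign of π that adds to the treatment effect. With the opposite sign the mean is 0.476, and the same formula gives Φ(2.814 − 2.278) = Φ(0.536), about 0.70.

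**Step 4: unequal sequences.** The paired-t contrast is shifted by π(n₁ − n₂)/35. At π = 0.5:

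| Split | shift in paired-t contrast (SD) | type I error, paired t | type I error, crossover |
|---|---|---|---|
| 18/17 | 0.5 × 1/35 = 0.014 | 0.029 | 0.050 |
| 20/15 | 0.5 × 5/35 = 0.071 | 0.044 | 0.050 |
| 21/14 | 0.5 × 7/35 = 0.10 | 0.058 | 0.050 |
| 22/13 | 0.5 × 9/35 = 0.129 | 0.078 | 0.050 |

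Near balance the paired t is conservative. It becomes anticonservative only at clear imbalance. Under simple 1:1 randomization (an assumption), a split of 21/14 or worse occurs in 31% of trials of 35.

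**Step 5: choosing the test after a normality check.** The plan gives no rule, so one was assumed: Shapiro-Wilk at 0.05 selects either the paired t or a normal test with bootstrap SE (n = 35, 40,000 trials each).

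| Distribution of differences | type I error with selection | paired t alone |
|---|---|---|
| normal | 0.050 | 0.049 |
| t, 5 df | 0.051 | 0.048 |
| moderate skew | 0.061 | 0.056 |
| exponential skew | 0.083 | 0.072 |

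**The case against.** The best defense is that the paired t is shorthand for the crossover model, as the Power Analysis section suggests, and that little turns on it. The plan does not expect a significant period effect, and the design leaves limited room for one. Boluses are automatic, meals are the same at both visits, staff run the sessions, and entry requires stable pump settings or doses. From 0 to 0.3 SD the power loss is about one point or less. Averaged over simple randomization, type I error of the paired t stays at 0.048 to 0.052. All of this stands and limits the size of the point. It does not settle which p-value is primary, and a period effect that is not significant can still move an unadjusted test.

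A reader might infer more than the documents support:

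- *The reported effect is biased.* It is not. The estimate comes from the adjusted model; only the paired-t contrast and its p-value take up the period effect.
- *The 0.05 level loses its meaning because the test is chosen from the data.* Under the assumed rule, selection adds about 0.5 to 1 point under skew and almost nothing for symmetric data. The fault is missing pre-specification.
- *An odd N makes imbalance a problem.* At 18/17 the shift is only π/35.
- *The plan's confidence interval contradicts its test.* The section specifies no interval.
- *Transformation should be ruled out.* That is a preference. What matters is that the scale is fixed beforehand.

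**Conclusion.** The inconsistency is in the text: estimation adjusts for period, the stated test does not, and the Power Analysis section treats the paired t only as an approximation to the adjusted model. It applies to both primary endpoints.

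The practical effect is conditional. With no period effect the mismatch costs almost nothing. With near-equal sequences and a period effect of 0.5 SD or more, which is at least as large as the 0.49 SD treatment effect, the test loses roughly 4 to 14 points of power over the range 0.5 to 0.8 SD (0.80 to 0.76, and 0.80 to 0.66). With clearly unequal sequences its error rate can exceed 0.05, and the direction of the shift depends on the sign of the period effect. All of these figures rest on assumed period effects and splits. The sample size justification is sound. The change is worth making because it is cheap and removes a real ambiguity.

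**What to change.** For each primary endpoint, take the estimate, 95% CI and p-value from the one crossover mixed model: treatment, period and sequence as fixed effects, participant as random. Name the analysis scale before the data are analyzed. Replace the paired-t sentence accordingly. Run a participant-level bootstrap, stratified by sequence and with period retained, as a sensitivity analysis whatever the diagnostics show.

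The cost is wording in the Statistical methods section and one degree of freedom (33 instead of 34). Power at 0.49 SD stays at about 80% with near-equal sequences and is about 79% at 21/14. N=35 stands, and no new data are needed.

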The clinical study described in this protocol is a safety and efficacy study in order to develop a non-hybrid, fully automated closed loop system that does not require the person to announce meals to the system, and which utilizes the hormone analog pramlintide in combination with insulin to potentially reduce the meal related hyperglycemia and increase the time spent in target range during the daytime.

Primary Objectives:

- To evaluate safety and efficacy of a fixed co-ratio insulin and pramlintide delivery strategy under closed loop control after a meal is detected by the meal detection algorithm
- To evaluate performance of the fully closed-loop system with (1) insulin+pramlintide as compared to (2) insulin-only as measured by incremental area under the curve (iAUC) in the 6 hours following the first meal period

Secondary Objective:

- To evaluate performance of the fully closed-loop system with insulin+pramlintide as compared to insulin-only for other glycemic outcomes

Study Hypothesis:

Our hypothesis is that pramlintide and insulin delivered after a meal by a closed loop system in response to automated meal detection will be well tolerated and will allow for a reduction in the postprandial glucose response as measured by the incremental area under the CGM curve (iAUC) compared with an insulin-only fully closed loop system.

Endpoints***Primary Endpoints:***

- Incremental area under the curve (iAUC) of postprandial glucose as measured by CGM in the 6 hours following the start of first meal. iAUC (mg/dL*min) will be calculated using a trapezoidal method [76], which sums all CGM values in the 6 hour period following the meal above the starting glucose.
- Percent of time with sensed glucose between 70 – 180 mg/dl in the 6 hours following the start of first meal.

Secondary Endpoints

- Incremental area under the curve (iAUC) of postprandial glucose as measured by CGM in the 6 hours following the start of second meal. iAUC (mg/dL*min) will be calculated using a trapezoidal method [76], which sums all CGM values in the 6 hour period following the meal above the starting glucose.
-

- Percent of time with sensed glucose between 70 – 180 mg/dl in the 6 hours following the start of second meal.

(The following secondary outcomes will be measured in the 6 hours following (1) the start of the first meal, (2) the start of the second meal, and (3) full study duration):

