- Protocol deviation having influence on efficacy or safety data as judged by the Investigator.
- Substantial and repeated non-compliance with trial procedures.
- Pregnancy. Intention of becoming pregnant.

Description of the MPC algorithms

Our exercise-aware model predictive control (exMPC) algorithm uses a glucoregulatory model to predict glucose outcomes over a predicted horizon (N_p), and mathematically solve for the optimal insulin doses across the control horizon (N_c) to bring the participant to target. The model is updated at each timestep by a Kalman filter, which uses the difference between CGM observations and model predictions to update the physiologic model states. Exercise is represented by heart rate data collected from a wrist-worn fitness watch. Elevated heart rate is represented by increased glucose disposal in the form of increased insulin sensitivity. In summary, a model-predictive controller uses a physiologic model to calculate how much insulin is required to bring someone to glucose target, and these predictions are adapted to the specific

participant using a Kalman filter. The exMPC algorithm has been described previously and has been clinically evaluated in multiple outpatient studies [79-81].

The Meal Detection feature in the algorithm includes a model for missed meal insulin detection and carbohydrate size estimation[2]. The model includes estimations for carbohydrate consumption based glucose patterns to determine if that person has consumed a meal without announcing it to the system. We refer to this algorithm as the Meal Detection algorithm.

Statistical methods

The primary study endpoints are (1) incremental area under the curve (AUC) of glucose in the 6 hours following unannounced meals and (2) percent of time with glucose sensor 70-180 mg/dL.

The hypothesis to be tested is that pramlintide and insulin delivered after a meal by a closed loop system in response to automated meal detection will improve postprandial glucose control over insulin delivered alone in response to automated meal detection.

Incremental AUC (iAUC) of postprandial glucose (mg/dL*min) will be calculated using a trapezoidal method which sums all CGM values in the 6 hour period following the meal above the starting glucose. (M. M. Tai, "A Mathematical Model for the Determination of Total Area Under Glucose Tolerance and Other Metabolic Curves," Diabetes Care, vol. 17, no. 2, p. 152, 1994, doi: 10.2337/diacare.17.2.152.)

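### Two primary endpoints are tested at two-sided 0.05 with no order, adjustment or success rule; separately, Statistical methods restates their time windows loosely

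*Combined protocol and SAP*

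**What the plan says.** **Endpoints section.** Two primary endpoints are listed with equal rank. The first is "Incremental area under the curve (iAUC) of postprandial glucose as measured by CGM in the 6 hours following the start of first meal". The second is percent time at 70-180 mg/dL, also limited to the period "in the 6 hours following the start of first meal". The second-meal versions of both measures are listed as secondary.

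**Statistical methods.** Both measures are again called primary, but in different words. For iAUC the text is "1) incremental area under the curve (AUC) of glucose in the 6 hours following unannounced meals"; for time in range it is "2) percent of time with glucose sensor 70-180 mg/dL", with no period attached. The hypothesis stated there is a general improvement in postprandial control and names no endpoint. The error rule for all tests is "We will use two-sided tests at the 0.05 level of significance".

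**Power Analysis.** With 35 participants the plan claims 90% power at 0.56 SD and "80% power to detect a 0.49-SD difference with a two-sided test at the .05 level of significance". The earlier result that supports the assumed effect is a 0.64-SD reduction in 4-hour postprandial AUC. No effect size or power is given for time in range.

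**Objectives and hypothesis.** The primary objective on system performance and the Study Hypothesis name iAUC as the efficacy measure. Neither mentions time in range.

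No section gives a testing order, an alpha split, a multiplicity method, or a rule on whether one or both endpoints must be significant.

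**The concern.** With two endpoints of equal standing, each tested at 0.05, the plan does not define primary success. A trial significant on one endpoint and not the other could be reported as positive, and the choice of reading would be made after the results are known. The 5% level that the plan sets for itself would then not be the chance of a false primary claim.

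The looser wording in Statistical methods is a second, separate problem. Each visit has two meals without a premeal bolus, so a plural reference to meals does not identify which 6-hour period is primary. Time in range with no stated period could be computed over the first meal, the second, or the whole visit.

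**Working it through.** **1. Reproduce the plan's power.** The inputs from Power Analysis are n = 35, a paired t test and two-sided alpha 0.05. Power is the probability that a noncentral t with 34 degrees of freedom and noncentrality d × √35 falls outside ±t(0.975; 34).

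- d = 0.56: noncentrality 0.56 × 5.916 = 3.31, power 89.6% (plan: 90%).
- d = 0.49: noncentrality 0.49 × 5.916 = 2.90, power 80.4% (plan: 80%).

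The stated figures are correct for one test at an undivided 0.05.

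**2. Error if either endpoint suffices.** Assume no true effect on either endpoint.

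- Independent tests: 1 − 0.95² = 9.75%.
- Upper bound under any dependence: 0.05 + 0.05 = 10%.
- Correlated tests, any two-sided rejection: 1 − P(|Z1| < 1.96 and |Z2| < 1.96), with Z1, Z2 bivariate normal.
- False claims of benefit only, both statistics oriented so that positive favors pramlintide: 1 − P(Z1 < 1.96 and Z2 < 1.96). Independent case: 1 − 0.975² = 4.9%.

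The documents give no correlation between the endpoints, so a range is shown.

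| Assumed correlation | Any two-sided rejection | Paired-t simulation, n = 35 | False claim of benefit only |
|---|---|---|---|
| 0 | 9.75% | 9.6% | 4.9% |
| 0.5 | 9.1% | 9.0% | 4.5% |
| 0.7 | 8.3% | 8.3% | 4.2% |
| 0.8 | 7.8% | 7.9% | 3.9% |
| 0.9 | 7.0% | 7.2% | 3.5% |

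For a single test the reference values are 5% and 2.5%. The simulation used 200,000 runs per correlation.

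**3. Error under other rules.** If both endpoints had to be significant, the error would be at most 5%. A fixed order, with the second endpoint tested only after the first succeeds, also holds it at 5% or less.

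**4. What the remedies cost at n = 35.**

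- Split of 0.025 + 0.025: power 82.8% at 0.56 SD and 70.9% at 0.49 SD. The detectable differences rise to 0.62 SD (90% power) and 0.54 SD (80% power). About 43 completers would restore the stated power.
- Fixed order: the first endpoint keeps the full 0.05, so its power stays as in step 1.
- Both required: joint power cannot be computed, because the plan gives no effect for time in range.

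**5. Windows, side by side.**

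| Measure | Endpoints section | Statistical methods |
|---|---|---|
| iAUC | 6 h from start of first meal | 6 h after unannounced meals, first meal not specified |
| Time in range | 6 h from start of first meal | no window |

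The figures in step 2 come from having two tests. The window mismatch contributes nothing to them.

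**The case against.** The strongest reply is that the plan never says either endpoint suffices. Statistical methods states one hypothesis, and if both endpoints were required the error would be at most 5%. That is correct, and it makes the inflation conditional. It does not remove the defect, because the plan does not say that both are required either.

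A second reply is that iAUC is the lead endpoint in all but name. The performance objective, the Study Hypothesis and the effect behind the sample size all rest on AUC, and Statistical methods twice refers to the primary outcome in the singular. This supports putting iAUC first. It is not a stated order, since the same section also uses the plural and both lists give the two measures equal rank.

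Third, this is a single-center study to develop a system, and nothing in the documents calls it confirmatory evidence for marketing. That bears on the consequences. The plan still sets a formal two-sided 0.05 level and powers the study on it.

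On the windows, a reader might infer that Statistical methods promotes the second-meal analyses to primary. That would make four tests, with an error of 1 − 0.95⁴ = 18.5% if independent and 20% at most. The documents do not support this. The Endpoints section expressly makes those analyses secondary, the iAUC calculation in Statistical methods reverts to a single meal, and the plural could mean a pooled measure or be loose wording.

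**Conclusion.** The concern holds in conditional form. The plan as written does not hold the primary error at 5%, because it leaves open that either of two endpoints, each tested at 0.05, may carry the primary claim. On that reading the family-wise error is about 7-9%. This assumes no effect on either endpoint and a correlation of 0.5 to 0.9, which is plausible because both are computed from the same CGM trace but is not given in the documents.

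A reader might take 10% as the trial's error rate. It is only the ceiling, and it needs near-independence as well as an either-endpoint rule. A reader might also think that the differing windows produce the excess, or that Statistical methods gives time in range a conflicting window. Neither is so: the excess comes from the two tests, and for time in range the window is omitted.

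The window mismatch stands as a separate inconsistency between two current sections. The power figures are right for one endpoint at 0.05, and their stated basis covers AUC only. Both matters should be settled before the data are analyzed, since a rule written afterwards would not protect the stated error level.

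**What to change.** 1. In Statistical methods, state a fixed sequence: first-meal 0-6 h iAUC at two-sided 0.05, then first-meal 0-6 h time in range at two-sided 0.05 only if iAUC is significant.
2. Replace the endpoint definitions in Statistical methods with those in the Endpoints section.
3. State in Power Analysis that the 90% and 80% figures apply to iAUC.

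This takes a few sentences and leaves the target of 35 completers and the iAUC power unchanged. The price is that time in range cannot be claimed as a primary success if iAUC fails; it can still be reported with its estimate and interval.

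Requiring both endpoints, or splitting alpha, would also control the error. The fixed sequence is preferred because it follows the plan's own objective, hypothesis and power basis, and avoids the loss of power or the larger sample that a split would bring.
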